10.2.2.2 Telephone Visit (Day 7)

Clinic staff will telephone subject to assess safety and to record concomitant medications/therapies. Staff will instruct subject on study drug application, advise subjects regarding permitted emollient(s) for use on nontreatment days (use of emollient(s) and/or sunscreen on study drug treatment days within 4 hours before or after study drug application is prohibited), and remind subjects that at least 24 hours must have elapsed since IP application before their next visit. Subjects should not apply IP on visit days until after the visit. An unscheduled clinic visit may be performed, if necessary.

10.2.2.3 Visit 3 (Day 14 ±5 days)

The following procedures will be performed on Day 14 in the study clinic:

1. Record responses to DLQI and EQ-5D Quality of Life Questionnaires.
2. Record concomitant medications and concomitant therapies.
3. Record vital signs (blood pressure and pulse).
4. Record IGA.
5. Record VIIS.
6. Record roughness assessment.
7. Record palm/sole assessment.
8. Record palm/sole assessment of fissuring
9. Record ectropion score.
10. Assess local tolerance.
11. Record AEs and review diary.
12. Collect a PK blood sample (all subjects).
13. Collect returned study drug tubes; confirm study drug compliance by weighing returned kits (tubes and boxes, but not leaflets) and reviewing diaries.

14. Instruct subject on study drug application, and advise subjects regarding permitted emollient(s) and/or sunscreen for use on nontreatment days; use of emollient(s) on study drug treatment days within 4 hours before or after study drug application is prohibited. Remind subjects that 24 hours must have elapsed since IP application before the subject's next visit. Subjects should not apply IP on visit days until after the visit.
15. Weigh new study drug kits (tubes and boxes, but not leaflets) and dispense enough additional study drug until next visit, and new diary.

10.2.2.4 Visit 4 (Day 30 ±7 days)

The following procedures will be performed on Day 30 in the study clinic:

1. Record responses to DLQI and EQ-5D Quality of Life Questionnaires.
2. Record concomitant medications and concomitant therapies.
3. Record vital signs (blood pressure and pulse).
4. Record IGA.
5. Record VIIS.
6. Record roughness assessment.
7. Record palm/sole assessment.
8. Record palm/sole assessment of fissuring
9. Record ectropion score.
10. At sites where the optional photographic substudy is conducted, take photographs of subjects who have provided informed consent for the substudy.
11. Assess local tolerance.
12. Record AEs and review diary.
16. Perform a 12-lead ECG
17. Perform a urine pregnancy test for WOCBP.
18. Collect blood and urine for routine laboratory tests (subject must be fasting at least 8 hours) and coagulation panel.
19. Collect a PK blood sample (all subjects).
20. Among subjects who consent to participate in the PK substudy, ensure that PK lines are placed before IP application. The IP will be applied in the clinic at this visit, and samples will be taken predose and at 1, 2, 4, 8, 12, and 24 hours postdose.
21. Among subjects in the PK study, perform an additional ECGs at times of serial sampling.
22. Collect returned study drug tubes; confirm study drug compliance by weighing returned kits (tubes and boxes, but not leaflets) and reviewing diaries.
23. Instruct subject on study drug application, and advise subjects regarding permitted emollient(s) and/or sunscreen for use on nontreatment days; use of emollient(s) on study drug treatment days within 4 hours before and after study drug application is prohibited.

Remind subjects that 24 hours must have elapsed since IP application before the subject's next visit. Subjects should not apply IP on visit days until after the visit.

24. Weigh new study drug kits (tubes and boxes, but not leaflets) and dispense enough additional study drug until next visit, and new diary.
25. Provide information about OLE option to study subject.

10.2.2.5 Telephone Visit (Day 45)

Clinic staff will telephone subject to assess safety and to record concomitant medications/therapies. Staff will instruct subject on study drug application, advise subjects regarding permitted emollient(s) and/or sunscreen for use on nontreatment days (use of emollient(s) on study drug treatment days within 4 hours before or after study drug application is prohibited), and remind subjects that 24 hours must have elapsed since IP application before the subject's next visit. Subjects should not to apply IP on visit days until after the visit. An unscheduled clinic visit may be performed, if necessary. Staff will remind subject about OLE option.

10.2.2.6 Visit 5 (Day 60 ±7 days)

1. Record responses to DLQI and EQ-5D Quality of Life Questionnaires.
2. Record concomitant medications and concomitant therapies.
3. Record vital signs (blood pressure and pulse).
4. Perform a urine pregnancy test for WOCBP.
5. Record IGA.
6. Record VIIS.
7. Record roughness assessment.
8. Record palm/sole assessment.
9. Record palm/sole assessment of fissuring
10. Record ectropion score.
11. Assess local tolerance.
12. Record AEs and review diary.
13. Collect a PK blood sample (all subjects).
14. Collect returned study drug tubes; confirm study drug compliance by weighing returned kits (tubes and boxes, but not leaflets) and reviewing diaries.
15. Weigh new study drug kits (tubes and boxes, but not leaflets) and dispense enough additional study drug until next visit, and new diary.
16. Instruct subject on study drug application, and advise subjects regarding permitted emollient(s) and/or sunscreen for use on nontreatment days; use of emollient(s) and/or sunscreen on study drug treatment days within 4 hours before and after study drug application is prohibited. Remind subjects that 24 hours must have elapsed since IP

application before the subject's next visit. Subjects should not apply IP on visit days until after the visit.

17. Provide information about OLE option.

10.2.2.7 Visit 6 (Day 90 ±7 days) or Early Termination

The following procedures will be performed on Day 90 in the study clinic:

1. Record responses to DLQI and EQ-5D Quality of Life Questionnaires.
2. Perform a limited physical examination.
3. Record vital signs (blood pressure and pulse).
4. Record concomitant medications and concomitant therapies.
5. Record IGA.
6. Record VIIS.
7. Record roughness assessment.
8. Record palm/sole assessment.
9. Record palm/sole assessment of fissuring.
10. Record ectropion score.
11. At sites where the optional photographic substudy is conducted, take photographs of subjects who have provided informed consent for the substudy.
12. Assess local tolerance.
13. Record AEs and review diary.
14. Perform a 12-lead ECG.
15. Perform a urine pregnancy test for WOCBP.
16. Collect blood and urine for routine laboratory tests (subject must be fasting at least 8 hours) and coagulation panel.
17. Collect a PK blood sample (all subjects).
18. Collect returned study drug tubes; confirm study drug compliance by weighing returned kits (tubes and boxes, but not leaflets) and reviewing diaries.

For subjects who successfully complete (i.e., have reliable visit attendance and compliance with IP application, in the investigator's opinion) the initial 90 days of double-blind treatment and choose to continue into the OLE, this visit will be the first visit of that portion of the study. All efficacy assessments, safety/tolerability assessments, including clinical laboratory testing, PK from Day 90 will be carried over to the OLE and will not be repeated. If the subject chooses to continue into OLE, the following additional procedures will be done:

1. Have the subject sign OLE-specific informed consent.
2. Measure subject's weight.

3. Instruct subject on study drug application, and advise subjects regarding permitted emollient(s) and/or sunscreen for use on nontreatment days; use of emollient(s) on study drug treatment days within 4 hours before or after study drug application is prohibited. Remind subjects that at least 24 hours must have elapsed since IP application before the PK draws at the Day 120 and Day 180 Visits, and not to apply IP on visit days until after the visits.
4. Weigh new study drug kits (tubes and boxes, but not leaflets) and dispense enough additional study drug until next visit (only for subjects who choose to continue into the OLE).
5. Dispense study diary.

10.2.3 Follow-up Telephone Call (± 14 days after Day 90) – Only Subjects Who Do Not Continue into Open-label Extension

Clinic staff will telephone subjects who choose not to continue into the Open-label Extension within 14 days after Day 90 to assess any ongoing AEs.

10.2.4 Open-label Extension

Subjects who successfully complete (i.e., have reliable visit attendance and compliance with IP application, in the investigator's opinion) the initial 90 days of double-blind treatment may choose to continue into an optional 90 day OLE with trifarotene cream HE1 200 $\mu\text{g/g}$. During the OLE, subjects will return to the site at Days 104, 120, 150, 180 and 194. Additional PK samples will be drawn at Days 120 and 180 from all subjects who continue into the OLE.

10.2.4.1 Telephone Visit (Day 97)

Clinic staff will telephone subject to assess safety (AEs) and to record concomitant medications/therapies. Staff will instruct subject on study drug application, advise subjects regarding permitted emollient(s) for use on nontreatment days (use of emollient(s) on study drug treatment days within 4 hours of study drug application is prohibited), and remind subjects not to apply IP on visit days until after the visit. An unscheduled clinic visit may be performed, if necessary.

10.2.4.2 Visit 7 (Day 104 ± 5 days)

The following procedures will be performed at this study clinic visit:

1. Record concomitant medications and concomitant therapies.
2. Record vital signs (blood pressure and pulse).
3. Record IGA.
4. Record VIIS.
5. Record assessment of roughness.
6. Record palm/sole assessment.
7. Record palm/sole assessment of fissuring.

8. Record ectropion score.
9. Assess and record local tolerance/AEs and review diary.
10. Collect returned study drug tubes; confirm study drug compliance by weighing returned kits (tubes and boxes, but not leaflets) and reviewing diaries.
11. Weigh new study drug kits (tubes and boxes, but not leaflets) and dispense enough additional study drug until next visit, and new diary.
12. Instruct subject on study drug application, and advise subjects regarding permitted emollient(s) for use on nontreatment days; use of emollient(s) and/or sunscreen on study drug treatment days within 4 hours before or after study drug application is prohibited. Remind subjects that 24 hours must have elapsed since IP application before the subject's next visit (Day 120), and if the Day 120 visit day coincides with a treatment day, wait until after the visit is complete to apply IP.

10.2.4.3 Visit 8 (Day 120 ±7 days)

The following procedures will be performed at this study clinic visit:

1. Record concomitant medications and concomitant therapies.
2. Record vital signs (blood pressure and pulse).
3. Record IGA.
4. Record VIIS.
5. Record assessment of roughness.
6. Record palm/sole assessment.
7. Record palm/sole assessment of fissuring.
8. Record ectropion score.
9. Assess and record local tolerance/AEs and review diary.
10. Perform a 12-lead ECG.
11. Perform a urine pregnancy test for WOCBP.
12. Collect blood and urine for routine laboratory tests (subject must be fasting at least 8 hours) and coagulation panel.
13. Collect a PK blood sample (all subjects)
14. Collect returned study drug tubes; confirm study drug compliance by weighing returned kits (tubes and boxes, but not leaflets) and reviewing diaries.
15. Weigh new study drug tubes and dispense enough additional study drug until next visit, and new diary.
16. Instruct subject on study drug application, and advise subjects regarding permitted emollient(s) for use on nontreatment days; use of emollient(s) and/or sunscreen on study drug treatment days within 4 hours before or after study drug application is prohibited.

10.2.4.4 Telephone Visit (Day 134)

Clinic staff will telephone subject to assess safety (AEs) and to record concomitant medications/therapies. Staff will instruct subject on study drug application, advise subjects regarding permitted emollient(s) and/or sunscreen for use on nontreatment days (use of emollient(s) on study drug treatment days within 4 hours of study drug application is prohibited), and remind subjects that 24 hours must have elapsed since IP application before the subject's next visit. An unscheduled clinic visit may be performed, if necessary.

10.2.4.5 Visit 9 (Day 150 ±7 days)

The following procedures will be performed at this study clinic visit:

1. Record concomitant medications and concomitant therapies.
2. Record vital signs (blood pressure and pulse).
3. Record IGA.
4. Record VIIS.
5. Record assessment of roughness.
6. Record palm/sole assessment.
7. Record palm/sole assessment of fissuring.
8. Record ectropion score.
9. Assess and record local tolerance/AEs and review diary.
10. Perform a urine pregnancy test for WOCBP.
11. Collect returned study drug tubes; confirm study drug compliance by weighing returned kits (tubes and boxes, but not leaflets) and reviewing diaries.
12. Weigh new study drug kits (tubes and boxes, but not leaflets) and dispense enough additional study drug until next visit, and new diary.
13. Remind subjects that 24 hours must have elapsed since IP application before the subject's next visit (Day 180) and if the Day 180 visit coincides with a treatment day, wait until after the visit is complete to apply IP.

10.2.4.6 Visit 10 (Day 180 ±7 days) or Early Termination

The following procedures will be performed at this study clinic visit:

1. Perform a physical examination.
2. Record vital signs (blood pressure and pulse).
3. Record concomitant medications and concomitant therapies.
4. Record IGA.
5. Record VIIS.
6. Assess roughness.

7. Record palm/sole assessment.
8. Record palm/sole assessment of fissuring.
9. Record ectropion score.
10. Assess local tolerance
11. Record AEs and review diary.
12. Perform a 12-lead ECG.
13. Perform a urine pregnancy test for WOCBP.
14. Collect blood and urine for routine laboratory tests (subject must be fasting at least 8 hours) and coagulation panel.
15. Collect a PK blood sample (all subjects)
16. Collect returned study drug tubes; confirm study drug compliance by weighing returned kits (tubes and boxes, but not leaflets) and reviewing diaries.

10.2.4.7 Follow-up Evaluation – Open-Label Extension (Day 194 or 14 days after End of Open label Treatment/Visit 11)

At 14 days after the last administration of the IP, the following procedures will be performed:

1. Perform a limited physical examination.
2. Record vital signs (blood pressure and pulse).
3. Record any concomitant medications/therapies.
4. Record IGA.
5. Record VIIS.
6. Assess roughness.
7. Record palm/sole assessment.
8. Record palm/sole assessment of fissuring.
9. Record ectropion score.
10. Assess and record AEs occurring since the last evaluation and review diary.
11. Perform a urine pregnancy test for WOCBP.

10.3. Assessments

The 5-point IGA is a valid measure of disease severity and meets the need for a clinically meaningful measure of success for ichthyosis studies. The IGA scale was developed with the support of experts from academic reference centers for the treatment of ichthyosis. Each level of severity will consider both the severity of scaling and the severity of roughness (Section 10.3.1.2). While retinoid treatment is expected to reduce scale, it may increase erythema; therefore, in this study, erythema will be evaluated as part of local tolerability.

10.3.1 Efficacy Variables

All efficacy measurements will use scales previously used for dermatological studies or as defined in the following sections.

10.3.1.1 Investigator's Global Assessment

The primary endpoint is the number of subjects in each treatment group who experience successful resolution of LI where "success" is defined as clear/almost clear and at least a 2-grade change from Baseline at Day 90/EOT in the Double-blind Period on a 5-point IGA full body scale.

The investigator will rate the subject's condition using the 5-point IGA at each time point shown in the Schedule of Events (Section 2.2).

The IGA will be measured on a 5-point scale, excluding the following areas: knees, elbows, neck, palms, soles, axillae, groin, and scalp:

0	Clear	No scaling and no roughness
1	Almost Clear	Occasional fine scales; hardly palpable roughness (mostly smooth)
2	Mild	Small and fine scales predominate; no more than a few large scales; mild roughness on palpation
3	Moderate	Some large scales that may be thick; coarse roughness on palpation
4	Severe	Confluent, primarily large (>1 cm), thick scales with plate-like hyperkeratosis

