
CRITERIA FOR EVALUATION
	
Primary efficacy endpoint: The proportion of subjects in each treatment group who experience successful resolution of LI where “success” is defined as clear/almost clear on treated areas and at least a 2-grade change from Baseline at Day 90/end-of-treatment (EOT) in the Double-blind Period on the 5-point IGA full body scale.
 
Secondary endpoints:
 
 – The difference in mean scores between the active trifarotene cream HE1 and vehicle groups in the following assessment indices from Baseline through Day 90: 
 – 5-point Visual Index for Ichthyosis Severity (VIIS) for scaling (overall 16 points for scaling, i.e., 0-4 points for 4 body areas: chest/abdomen, back, arms, and legs) – Individual score for roughness (Scale: 0–4) – Palm/sole Assessment (Scale: 0–4) – Quality of life per Dermatology Life Quality Index (DLQI) – The difference in proportion of subjects with presence of fissures on palms/soles (presence/absence, number of fissures, and pain associated with fissures on a 0-3 scale) at Day 90 between the active trifarotene cream HE1 and vehicle groups 
Exploratory endpoints:
 
 – The difference in mean ectropion (Ectropion Severity Score [ESS] of 0–8) scores between the active trifarotene cream HE1 and vehicle groups from Baseline through Day 90 – The difference in quality of life per EQ-5D-5L score between the active trifarotene cream HE1 and vehicle groups from Baseline through Day 90 
Safety endpoints:
 
 – Reported serious adverse events (SAEs), treatment-emergent AEs (TEAEs), and changes in clinical laboratory tests, vital signs, physical examinations, and 12-lead ECGs – Local tolerability (stinging/burning, pruritus, or erythema on: 0-3 scales [none, mild, moderate, severe]) for each body area (chest/abdomen, back, legs, arms, and face/neck) 
Pharmacokinetic endpoints: Plasma concentrations of CD5789 and its major metabolites will be measured.

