7. STUDY DESIGN

7.1. Overall Study Design and Plan

The first part of this study is a phase 2, randomized, 2-cohort, double-blind, vehicle-controlled, multicenter study of the safety, tolerability, PK, and efficacy study of trifarotene cream HE1 100 µg/g and 200 µg/g in subjects with LI for 90 days. Subjects who complete the randomized, double-blind, vehicle-controlled period of the study will be eligible to continue into an open-label extension (OLE) and be treated with trifarotene cream HE1 200 µg/g for an additional 90 days.

The randomized, double-blind, vehicle-controlled period of the study in subjects with moderate to severe LI (i.e., 3–4 on a 5-point Investigator Global Assessment [IGA] scale where 0 = clear; 1 = almost clear; 2 = mild; 3 = moderate; and 4 = severe), is designed to compare the safety of 2 doses of trifarotene cream HE1 with that of vehicle in the treatment of LI.

Upon signing informed consent and entering the Screening Period, subjects will stop using physical and medical treatments for LI, including balneotherapy, and may begin to washout prohibited topical and systemic treatments with designated washout periods (Table 9-2), as applicable. Washout may be up to 90 days, as necessary.

During washout, subjects may continue taking their standard of care of visible skin (face and scalp) for cosmetic reasons and of extremities (palms/soles) to avoid functional consequences on walking or moving their fingers. In the US/EU, this may include compounded emollients with keratolytics (alpha or beta hydroxyl acids) and/or urea. The investigator should approve and document these standard-of-care treatments in the electronic case report form (eCRF). If the standard of care treatments of the face and/or palms/soles contain prohibited medications, they must be stopped at the Baseline Visit. Subjects may shower, but not bathe or swim. The IGA will be evaluated on the rest of the body at Baseline. After completing any necessary washout of prohibited medications, subjects will return to the site to have their LI assessed and to complete the study eligibility requirements.

Study drug will be packaged in 50-g tubes from which up to 36 g of IP may be dispensed per application, i.e., the maximum dose per application.

Study staff will choose 1 tube from the kit dispensed to the subject at that visit, and apply the first dose of study drug to each subject in the clinic on Day 1 after Baseline measurements; they will

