weigh the study tube before and after application to determine the amount used. If the product will be applied at home by someone other than the study subject, it is recommended that person assist with application at the first visit to learn how the IP is applied.

The kit dispensed at baseline must be weighed before the first tube is chosen for application by the study staff. Weight of the kits dispensed and returned by the subject during the study includes both tubes and cartons, but not leaflets, which need to be removed before weighing. The subject must be reminded to return the kits with tubes and cartons, whether used or not, when returning to the next visit.

Thereafter, subjects will apply up to 36 g of study drug on up to 90% of BSA twice weekly, sparing the scalp, inguinal, and axillary areas. Subjects with heavy facial hair should not apply IP to hair-bearing areas. Subjects will receive an adequate number of tubes to use 1 tube per application and will use a new tube for each treatment day. Subjects may use less than the full amount of IP in a tube.

The study protocol limits application of IP to 36 g maximum; no additional tubes can be given, whether during the randomization period or the OLE period. If the study staff and subject note that there is insufficient volume for full body application, the subject should apply trifarotene cream sparingly twice weekly to the most affected areas, and always to the same skin areas. Study cream should be very sparingly applied. Trifarotene cream 100 or 200 µg/g, is a highly potent topical retinoid and it is not necessary to apply much for efficacy; application of more will increase the risk of irritation and systemic penetration.

Enrolled subjects will receive treatment for 90 days.

The first cohort of subjects (Cohort A) will randomize adults (≥ 18 years old) in a 1:1:1 ratio to trifarotene (CD5789) cream HE1 100 µg/g, trifarotene cream HE1 200 µg/g, or vehicle.

After the initial 15 subjects complete at least 28 days of treatment, an independent DSMB will review aggregate safety and tolerability data (including PK and electrocardiogram [ECG] data). If no safety issues are identified, additional subjects will be allowed to enroll in Cohort B. Subjects in Cohort B will be randomized 1:1:1 to trifarotene cream HE1 100 µg/g, trifarotene cream HE1 200 µg/g, or vehicle and similarly treated twice weekly for up to 90 days in the same manner as subjects in Cohort A.

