Efficacy will be assessed by the number of subjects in each treatment group who achieve “success” defined as clear/almost clear overall and at least a 50% reduction from Baseline at Day 90/end-of-treatment (EOT) in the Double-blind Period on the 5-point IGA scale (i.e., 0 = clear; 1 = almost clear; 2 = mild; 3 = moderate; 4 = severe). In addition, efficacy criteria include assessment scales for palm/sole, scaling, roughness, fissuring, and the Dermatology Life Quality Index (DLQI), and the EQ-5D Quality of Life (QoL) Questionnaire. Ectropion Severity Scores (ESS) between the active trifarotene cream HE1 and vehicle groups will be an exploratory endpoint.

Plasma concentrations of CD5789 and its major metabolites will be measured.

Safety will be assessed by evaluating reported adverse events (AEs), changes in clinical laboratory test results, vital sign measurements, physical examinations, 12-lead ECGs, and local tolerability (stinging/burning, pruritus, or erythema on 0-3 scales [none, mild, moderate, severe]).

All AEs observed by the study personnel or reported by the subject during the study (from the time of the signing of the informed consent through the post-treatment visit) will be documented.

Topical trifarotene cream HE1 was generally well tolerated in recently completed phase 3 pivotal and long-term safety studies in subjects aged 9 years and older with acne vulgaris. The local tolerability of the trifarotene cream HE1 formulation in subjects with LI is unknown and will be monitored during the study. Subjects will receive information on study drug use and stopping rules and will be instructed to contact the site with any safety/tolerability issues. Study personnel will telephone subjects in between scheduled visits (i.e., at Day 7 and Day 45) to assess safety; an unscheduled clinic visit may be performed, if necessary. At each clinic visit, the investigator will assess local tolerability (stinging/burning, pruritus, or erythema on 0-3 scales [none, mild, moderate, severe]) on each treated body area (chest/abdomen, back, legs, arms, and face/neck).

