9.8.1 Permitted Therapies

Subjects will be advised on permitted emollient(s) for use as often as needed on nontreatment days during the study; on treatment days, the use of emollient(s) is permitted except within 4 hours before or after study drug application. Similarly, protective sunscreen should be applied as often as needed, except within 4 hours before or after study drug application. Subjects may use their standard of care treatment on their faces and/or palms/soles after the Day 30 assessment if they

experience a worsening of IGA in those areas. In the US/EU, this may include compounded emollients with keratolytics (alpha or beta hydroxyl acids) and/or urea. These standard of care treatments should be approved by the investigator and documented in the eCRF.

Subjects who enter the OLE must stop standard of care treatment. If they experience a worsening of IGA they may use standard of care treatment on their faces and/or palms/soles after the Day 120 Visit if the standard of care does not contain prohibited medications. If those standard of care treatments include prohibited medications, the subject should be discontinued from the study.

Other concomitant medications are allowed (e.g., analgesics, antihistamines), but should be limited to those medications considered necessary. All concomitant medications, both prescribed and over-the-counter, should be recorded in the eCRF.

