13.1.4.1 Efficacy Endpoints

Primary efficacy endpoint: The proportion of subjects in each treatment group who experience successful resolution of LI where “success” is defined as clear/almost clear overall and at least a 2-grade change from Baseline at Day 90/EOT in the Double-blind Period on the 5-point IGA scale.

Secondary: The secondary endpoints are as follow:

- The difference in mean scores between the active trifarotene cream HE1 and vehicle groups in the following assessment indices from Baseline through Day 90:
 - 5-point VIIS scale for scaling
 - Individual score for roughness (Scale: 0–4)
 - Palm/sole Assessment (Scale: 0–4)
 - Quality of life per DLQI
- The difference in proportion of subjects with presence of fissures on palm/soles (presence/absence, number of fissures, and pain associated with fissures [on a 0-3 scale]) at Day 90 between the active trifarotene cream HE1 and vehicle groups

Exploratory: The exploratory endpoints are as follow:

- The difference in mean ectropion scores (ESS of 0–8) between the active trifarotene cream HE1 and vehicle groups from Baseline through Day 90
- The difference in quality of life per EQ-5D-5L scores between the active trifarotene cream HE1 and vehicle groups from Baseline through Day 90

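### The protocol describes the skin rated for the primary IGA endpoint in conflicting ways, so Baseline and Day 90 need not cover the same areas

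*Protocol*

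**What the plan says.** All of the following is current protocol text, not the amendment log.

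- **Synopsis (2.1), primary endpoint:** success is "clear/almost clear on treated areas and at least a 2-grade change from Baseline", and the same sentence places it "in the Double-blind Period on the 5-point IGA full body scale".
- **Section 7.1:** success is "clear/almost clear overall and at least a 50% reduction from Baseline".
- **Section 13.1.4.1:** success is "clear/almost clear overall and at least a 2-grade change from Baseline at Day 90/EOT".
- **Section 10.3.1.1:** a full-body scale, followed by "The IGA will be measured on a 5-point scale, excluding the following areas: knees, elbows, neck, palms, soles, axillae, groin, and scalp". The rating is to be made at each time point in the Schedule of Events, which includes Screening and Baseline.
- **Sections 7.1, 9.8 and 10.2.1.1.1:** after naming face, scalp, palms and soles as areas where standard of care may continue during washout, each section says "The IGA will be evaluated on the rest of the body at Baseline". No section gives a matching rule for Day 90.
- **Section 7.1, when there is too little cream for the whole body:** "the subject should apply trifarotene cream sparingly twice weekly to the most affected areas, and always to the same skin areas".
- **Section 9.8.1:** "Subjects may use their standard of care treatment on their faces and/or palms/soles after the Day 30 assessment", on condition that the IGA has worsened in those areas.

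The adult-and-adolescent version of the protocol in the same file has the same wording wherever the corresponding sections are shown.

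**The concern.** Success combines an absolute Day 90 grade with a change from Baseline, so both ratings must refer to the same skin. The IGA 3–4 entry criterion depends on the rated field as well. The IGA is a single global grade given by the investigator at the visit. No area sub-scores are specified, whereas the VIIS names four areas. Once a rater has included or left out the face, the analysis cannot undo it. Photographs are optional, the central reader serves only as a quality check, and Section 13.1.4 bases efficacy on investigator assessment. With about 40 sites planned, an undefined field leaves room for the same patient to be classified differently from one site to another.

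**Working it through.** **1. The area rules side by side**

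| Place | Field | Face | Palms, soles | Knees, elbows, neck |
|---|---|---|---|---|
| 2.1 | treated areas, on a full-body scale | in, if treated | in, if treated | in, if treated |
| 7.1, 13.1.4.1 | overall | not stated | not stated | not stated |
| 10.3.1.1, every IGA visit | full body minus eight areas | in | out | out |
| 7.1, 9.8, 10.2.1.1.1, Baseline only | rest of the body | out | out | in |

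Three conflicts follow.

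- *Face.* At Baseline, 10.3.1.1 rates it and the other three sections leave it out. At Day 90 only 10.3.1.1 speaks, and it rates the face. A site using the Baseline-specific rule compares a Baseline grade without the face with a Day 90 grade that includes it.
- *Treated areas.* Section 7.1 spares only the scalp, inguinal and axillary areas. Knees, elbows, neck, palms and soles may therefore be treated but are not rated under 10.3.1.1. For a subject whose cream does not cover the whole body, some rated skin is untreated, so *treated areas* and *overall* can give different success calls.
- *Section 9.8.1.* It relies on a worsening of IGA on face and palms/soles. Section 10.3.1.1 removes palms and soles from the IGA, and the Baseline rule gives the face no starting grade.

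The 50% reduction in 7.1 adds no further conflict over who succeeds. From an eligible Baseline of 3 or 4, reaching grade 1 is a drop of 2 or 3 grades, and a reduction of 2/3 = 67% or 3/4 = 75%. Grade 0 is a larger drop in each case. Both criteria are therefore met whenever the subject is clear or almost clear.

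**2. The plan's own figure**

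Section 13.2 assumes 70% v 40% success, 32 evaluable per arm (120/3 × 0.8) and a two-sided Fisher's exact test, and states power above 80%. With alpha 0.05 from Section 13.1, enumerating all outcomes of two independent binomials with n = 32 gives 61.9%. The stated figure is not reproduced. That is a separate matter; 61.9% serves here only as the starting point.

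**3. Illustration of size**

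The documents give no misclassification rate, so the values of m below are assumptions.

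Model A, random flips in both directions: p′ = p(1 − m) + (1 − p)m. Example for m = 0.10: 0.70 × 0.90 + 0.30 × 0.10 = 0.66, and 0.40 × 0.90 + 0.60 × 0.10 = 0.42.

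Model B, a share of successes becomes failures, equally in both arms: p′ = p(1 − m). Example for m = 0.10: 0.63 and 0.36.

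| m | A: rates | A: difference | A: power | B: rates | B: difference | B: power |
|---|---|---|---|---|---|---|
| 0 | 0.70 v 0.40 | 30 points | 61.9% | 0.70 v 0.40 | 30 points | 61.9% |
| 0.05 | 0.68 v 0.41 | 27 | 52.0% | 0.665 v 0.38 | 28.5 | 56.9% |
| 0.10 | 0.66 v 0.42 | 24 | 42.0% | 0.63 v 0.36 | 27 | 51.9% |
| 0.20 | 0.62 v 0.44 | 18 | 24.4% | 0.56 v 0.32 | 24 | 42.0% |

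All powers are exact two-sided Fisher at 32 per arm.

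**The case against.** The best defence is that Section 10.3.1.1 is the only place that gives raters both a scale and an area list, and that it covers every visit, Baseline included. On that view *overall* and *full body* in the other sections are shorthand for a global score. This has force. It means Baseline has two competing rules, and it is not established that the two visits rate different skin. A reader might infer that the face is always out at Baseline and in at Day 90, but the documents show only that this can happen. The defence does not remove the conflict: three sections repeat the Baseline-specific rule, and nothing ranks one rule above the other. Nor can *treated areas* be read as shorthand for the 10.3.1.1 list, because the two sets differ.

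A reader might also infer that standard of care on the face would be used more in the vehicle arm and so shrink the drug–vehicle difference. The documents do not support this. The area rule is the same in all arms. Section 9.8.1 allows that care only after Day 30 and on worsening, with investigator approval and eCRF documentation. No usage rates are given.

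Finally, the power figures depend on the model. At 20%, Model A gives 24% and Model B gives 42%. They show sensitivity and are not an estimate.

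**Conclusion.** The point holds as an internal contradiction about the sole primary endpoint. The rated field is described in ways that cannot all be followed, Baseline has two rules for the face, and Baseline and Day 90 need not rate the same skin. This rests on the text alone and needs no numerical assumption. The consequence shown is an unclear endpoint with a risk of misclassification, not a demonstrated bias between arms. The size is unknown. Under assumed rates of 5% to 20%, power falls from 62% to 52–24% with random misclassification, or to 57–42% if successes are lost equally in both arms. The field should be settled before further subjects are rated, because a single global grade cannot be re-scored at analysis.

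**What to change.** Define one IGA scoring field, state whether the face is in or out, and use it at Screening, Baseline and every later visit, scored whether or not each included area received cream. Leaving the face out is the option that keeps skin under permitted standard of care out of the primary endpoint; its price is that the endpoint then says nothing about the face.

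Put identical words in Sections 2.1, 7.1, 9.8, 10.2.1.1.1, 10.3.1.1 and 13.1.4.1. Sections 9.8 and 10.2.1.1.1 must be included, because both repeat the Baseline-only sentence. Reconcile the reference in 9.8.1 to a worsening of IGA on face and palms/soles with the chosen field. Add the field to the IGA form and to rater training.

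No rule counting users of standard of care as failures is needed for this repair: with the face out, none of the areas where 9.8.1 permits that care is rated.

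The cost is a wording amendment, a form header and a training note, plus a sensitivity analysis for IGAs already scored under the present text.
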